Tetanus	anti-TTIgG	 All ages, incl. 65+ 	Classic marker of vaccination coverageUnclear population immunity in elderly	
Diphtheria	Anti-DT	•	 2022-2023 outbreak in Belgium including 1 fatal case (16y) Emergence of macrolide-resistant C. Diphtheria C. Ulcerans infections in elderly 	Risk groups Belgium 2014- 2016 Belgium, 2012
CMV	anti-CMV IgG	all ageswomen reproducti ve age	 Ph3 clinical trials vaccine underway cCMV big public health impact 	Belgium 2002,2006

Appendix 2

Data collection sheet for laboratories (only seen by laboratories)

Laboratory	Nb	1
------------	----	---

Unique code	Sample date	Date of birth	Gender	Postcode
Laboratory/gender/age				
Data collection sheet delivered i	from laboratories to Scier	nsano		
Laboratory Nb 1				
Unique code	Sample A date	\ge Ge	nder Arro	ondissement
Laboratory/gender/age				

Appendix 3

Dummy tables

1. Study population characteristics

Variable	Category	N (%) – Study population	N (%) – Belgian population
Age	1-4 yo		
	5-9 yo		
	10-14 yo		
	15-19 yo		
	20-29 yo		
	30-39 yo		
	40-49 yo		
	50-59 yo		
	60-69 yo		
	≥ 70 yo		
Sex	Female		
	Male		
Provinces	Antwerp		
	West Flanders		
	East Flanders		
	Limburg		
	Flemish Brabant		
	Walloon Brabant		
	Hainaut		
	Namur		
	Liege		
	Luxembourg		
	Brussels		

2. Seroprevalence by Demographic Characteristics – one table per pathogen

Characteristic	n tested	n seropositive	% Seropositive (95% CI)
Age group (years)			
Sex			
Region/provinces			

3.	Comparison of Seroprevalence over time (with previous seroprevalence study) – one table
	per pathogen

Birth cohort	Time point	n tested	n seropositive	% Seropositive (95% CI)
Targeted by measles vaccination	Study 2013/2015			
	Study 2025/2026			
Not targeted by measles vaccination	Study 2013/2015			
	Study 2025/2026			

4. Log binomial regression analysis (Prevalence Ratios) – one per pathogen

Variable	Adjusted Prevalence Ratios (95% CI)	p-value
Age		
Sex		
Region/provinces		

Appendix 4

Scientific steering committee – Composition

Function/entity	Expertise	Number of representatives
FOD Volksgezondheid (federal authorities)	Public Health	1
DepZorg (regional authorities)	Public Health	1
AViQ (regional authorities)	Public Health	1
Vivalis (regional authorities)	Public Health	1
ONE (regional entity)	Public Health (vaccination)	1
University of Hasselt – University of Antwerpen	Biostatistics	2
University of Gent (UGent) – University Hospital of Gent (UZ Gent)	Infectious diseases (adults)	1
University of Brussels (ULB) - University Hospital of St Pierre	Infectious diseases (adults)	1
Catholic University of Louvain-la- Neuve (UCL) – University Hospital of Dinant Godinne UCL Namur	Infectious diseases (children)	1
University Hospital of Brussel (UZ Brussel)	Infectious diseases (children)	1
University of Brussels (ULB) – Plotkin institute	Immunology	1
Sciensano	Public Health	3
	Biostatistics	
	Microbiology	
Representatives of the Epilabo network	Clinical microbiology	7

Scientific steering committee - Role

Provide input and feedback on main aspects as study, such as

- Choice of pathogens and priority research questions
- Methodology aspects
- Any technical issues that might arise
- Interpretation of results and preparation of communication and publication
- If applicable, evaluate external demands on the use of the serumbank

To be able to fulfill this role, it is expected that the selected committee members will participate to ca. 1 meeting / year in addition to provide ad-hoc written input (through e-mail) if required.

Appendix 5

Allocation of serological samples

The distribution of age-stratified samples follows the simulation-based framework developed by Blaizot et al. (2019) [1]. More specifically, the procedure aims to optimize the precision with respect to seroprevalence estimators (based on single cross-sectional serological survey data) for a fixed total sample size (i.e., number of blood serum samples collected in a random fashion). Using statistical and mathematical models, we compare several age-based sampling structures: (i) a survey-based age distribution corresponding to the observed age patterns in previous serological surveys, (ii) a population-based structure proportional to the current demographic age distribution, and (iii) a uniform age structure with equal sampling probabilities across different age groups. These strategies will be evaluated to determine which approach provides the most accurate and precise seroprevalence estimates. In addition, we compute the optimal number of samples to allocate within each age group in order to minimise uncertainty in the final estimates. We apply this method to three pathogens—measles virus, hepatitis B virus and cytomegalovirus—selected for their distinct sero-epidemiological profiles and the availability of historical serological data. These pathogens provide representative models for the wider range of infections covered by the multiplex test.

For measles, the most recent national serological survey was conducted in 2013. To estimate the current seroprevalence by age, we used a cohort-based modelling approach to project immunity levels to 2025. This model incorporates historical vaccination coverage information, age at which vaccination occurred and waning of humoral immunity, following methods described by Hens et al. (2015) and Abrams et al. (2016) (see [2], [3], respectively).

1. Materials and methods

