All laboratories (n=52) from Epilabo will be invited to participate to the collection of samples for this seroprevalence study. Depending on the number of laboratories agreeing to participate and to ensure geographical representativeness, participating laboratories will be allocated a fixed number of age-specific leftover samples to collect proportional to the population density in that area. To ensure equal proportion of males and females within the same age group, the number of samples to collect by the laboratories will equally be stratified by sex.

Sample size

The distribution of age-stratified samples will follow the simulation-based framework developed by Blaizot et al (2019), which aims to optimize the precision of seroprevalence estimates for a fixed total sample size (29). Using statistical and mathematical models, we will compare several age-based sampling structures: (i) a survey-based distribution corresponding to the age patterns observed in previous serological surveys, (ii) a population-based structure proportional to the current demographic distribution, and (iii) a uniform structure with equal sampling between age groups. These strategies will be evaluated to determine which provides the most accurate and precise seroprevalence estimates. In addition, we will compute the optimal number of samples to allocate within each age group in order to minimize uncertainty in the final estimates. We apply this method to two pathogens — measles virus and hepatitis B virus — selected for their distinct sero-epidemiological profiles and the availability of historical serological data. These pathogens provide representative models for the wider range of infections covered by the proposed seroprevalence study.

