For measles, the most recent national serological survey was conducted in 2013. To evaluate the sample size needed to estimate the current seroprevalence by age, we use a cohort-based modelling approach to project immunity levels to 2025. This model incorporates historical vaccination coverage, age of vaccination and waning immunity, following methods described by Hens et al. (2015) and Abrams et al. (2014) (30,31). The aim was to obtain both overall and agegroup-specific seroprevalence estimates with a precision of +-2% (width of confidence interval max. 4%). To ensure sufficient sample size of the serumbank for pathogens other than measles, these calculations were repeated for 2 additional pathogens. The additional pathogens (CMV and Hepatitis B) were selected based on their seroprevalence patterns in the population who differ importantly from the measles seroprevalence patterns.

Appendix 5 contains the full methodology and results. With a total sample size of 3,900 samples, precision of overall national seroprevalence estimates for all 3 pathogens would be <2% (and even <1% for measles and Hepatitis B). Not all agegroup-specific estimates would have <2% precision, but all are within acceptable ranges (all <3% precision for measles). To obtain equal precision in the region-specific estimates, similar absolute number of samples would need to be collected from Flanders, Walllonia and Brussels. However, as both the population size as well as

the number of labs in Brussels is much smaller than in Flanders, this is deemed unfeasible. We therefore plan a pragmatic approach and adjust the regional allocation to reflect practical constraints and the actual number of participating laboratories, accepting wider confidence intervals in Brussels. The final distribution of samples by agegroup is then presented in Table 1.

Table 1. Samples distribution - National

Age groups	Number of samples - National
1-4yo	450
5-9yo	450
10–14yo	300
15-19yo	450
19-31yo	450
31-40yo	750
40-65yo	1050
Total	3900

Sample collection and analysis

Sample collection and transport

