2.3. Allocation of samples for CMV

We estimated age-specific cytomegalovirus (CMV) seroprevalence using data from the 2011 Belgian serological survey. Figure S5 displays the observed seroprevalence and the fitted estimates obtained from a GAM. These model-based estimates were used to simulate the precision of overall CMV seroprevalence under various sample sizes and sampling strategies.

Figure 9 summarizes the results from 500 simulations, showing the mean, median, and 95% confidence intervals of overall seroprevalence across four total sample sizes (1,000 to 9,000) and three sampling structures (survey-based, population-based, and uniform). The three sampling designs yielded very similar results. The population-based structure showed slightly better precision at 1,000 samples, whereas the survey-based design performed best at 3,000 samples.

Based on these results, we recommend allocating at least 1,000 samples per region for CMV, corresponding to 3,000 samples nationally. With this total sample size, the estimated precision for the overall CMV seroprevalence at the national level ranges between $\pm 2.8\%$ and $\pm 3.4\%$, depending on the sampling strategy. Although this is sufficient for generating national estimates, it does not provide acceptable precision for regional-level estimates. To ensure adequate precision at the regional scale (e.g., $\pm 2\%$), a higher number of samples per region would be required. Detailed precision values for each sample size and sampling design are provided in Supplementary Table S3.

[figure not shown]

Figure 9. CMV serological data: mean, median and 95% confidence interval for the overall seroprevalence over 500 simulations as a function of the total number of sampled individuals.

3. Conclusions

We recommend allocating 3,900 samples nationally, corresponding to approximately 1,300 samples per region (Flanders, Brussels, and Wallonia), to ensure acceptable precision (below $\pm 2\%$) for estimating the overall seroprevalence of measles, hepatitis B, and CMV at the regional level.

An optimisation algorithm was used to test multiple age-based sampling distributions and identify the most efficient allocation for each pathogen. Table 2 summarises the optimal proportions of samples by age group, which differ slightly across pathogens. These proportions were then translated into absolute sample counts (Table 3), assuming 3,000 samples per pathogen at the national level.

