To ensure sufficient precision for all pathogens, we selected the maximum number of samples per age group across the three pathogens as the final recommendation. This results in a total of 3,900 samples nationally, which we divide equally across the three regions, yielding 1,300 samples per region.

Table 4 reports the expected precision of the overall seroprevalence estimates under this allocation. At the national level (3,900 samples per pathogen), the expected precision is 0.82% for measles, 0.85% for hepatitis B, and 1.69% for CMV. At the regional level (1,300 samples per region), expected precision decreases slightly to 1.69% for measles, 1.45% for hepatitis B, and 2.64% for CMV, still within acceptable bounds.

Age group	Measles	НерВ	CMV
1-4yo	5%	5%	15%
5-9yo	15%	15%	5%
10-14yo	5%	10%	10%
15-19yo	15%	5%	10%
19-31yo	15%	10%	10%
31-40yo	20%	25%	15%
40-65yo	25%	30%	35%
Precision	0,88%	0,74%	1,52%

Table 2. Optimal proportion of samples per age group for measles, hepatitis B, and CMV based on national-level simulations.

	Measles	НерВ	CMV	National	Regional
1-4yo	150	150	450	450	150
5-9yo	450	450	150	450	150
10-14yo	150	300	300	300	100
15-19yo	450	150	300	450	150
19-31yo	450	300	300	450	150
31-40yo	600	750	450	750	250
40-65yo	750	900	1050	1050	350
Total	3000	3000	3000	3900	1300

Table 3. Absolute number of samples per age group, assuming 3,000 samples per pathogen. The final allocation (bold values) corresponds to the highest required count across pathogens, resulting in a total of 3,900 samples nationally (or approximately 1,300 per region).

	Measles	НерВ	CMV
National	0,82%	0,85%	1,69%
Regional	1,69%	1,45%	2,64%

Table 4. Expected precision (half-width of the 95% simulation-based confidence interval) for overall seroprevalence estimates under the final allocation. National precision is based on 3,900 samples; regional precision is based on 1,300 samples per region.

Precision by age - national allocation

_	.=			
Age group	Allocation	Measles	НерВ	CMV
1-4yo	450	2,25%	0,50%	4,23%
5-9yo	450	2,61%	0,53%	3,25%
10-14yo	300	1,76%	0,63%	3,50%
15-19yo	450	1,95%	0,73%	3,14%
19-31yo	450	2,88%	1,20%	2,94%
31-40yo	750	2,40%	1,51%	2,78%
40-65vo	1050	1,25%	1.42%	3.02%

Table 5. Expected precision (half-width of the 95% simulation-based confidence interval) for prevalence estimates of each age group under the final allocation.

4. References of Appendix 5

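### Laboratory quotas are tied to population density, which does not serve geographical representativeness, and the only stated regional precision rests on an equal split that the main text rejects

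*Protocol*

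**What the plan says.** Three places in the protocol deal with how samples are spread geographically.

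- **Sampling procedure.** The quota rule opens with "Depending on the number of laboratories agreeing to participate and to ensure geographical representativeness" and continues that "participating laboratories will be allocated a fixed number of age-specific leftover samples to collect proportional to the population density in that area". The unit of area is not defined.
- **Sample size.** The section notes that equal precision by region would need similar numbers from the three regions. It judges this not feasible because Brussels has a smaller population and fewer laboratories. It will instead "adjust the regional allocation to reflect practical constraints and the actual number of participating laboratories, accepting wider confidence intervals in Brussels".
- **Appendix 5, section 3 (Conclusions).** "This results in a total of 3,900 samples nationally, which we divide equally across the three regions, yielding 1,300 samples per region". The Regional column of Table 3 and the Regional row of Table 4 rest on that figure. The same section justifies the 3,900 by precision below ±2% at regional level for measles, hepatitis B and CMV.

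Table 1 in the main text gives the age distribution nationally only. No place gives a planned number per region, a density, a surface area, or a count of laboratories by region. The only laboratory count is the 52 invited.

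**The concern.** Density is the wrong size measure for the stated purpose. A sample mirrors where people live when quotas follow the number of people in each area, not the number per square kilometre. A small, dense area gets a large quota under a density rule and a small one under a population rule. The quota rule and the Sample size section therefore point in opposite directions for Brussels if the first is read as written.

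The second problem is that the only regional precision in the protocol belongs to an allocation that the main text declines. The Sample size section refers the reader to Appendix 5 for full methodology and results, and nothing in the appendix marks the equal split as not adopted.

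Region matters to this study. The objectives ask for measles seroprevalence by geographical area and name region as a risk factor for susceptibility, and the analysis compares geometric mean titres by region. The background section reports second-dose coverage of 89% in Flanders against 75% in Wallonia and Brussels, and singles out Brussels as the place where coverage data will remain incomplete. Too few samples in a region cannot be repaired once collection has ended.

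**Working it through.** **1. The plan's own figures.** Taking the largest of the three pathogen columns in each row of Appendix 5, Table 3:

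450 + 450 + 300 + 450 + 450 + 750 + 1,050 = 3,900, and 3,900 / 3 = 1,300.

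Both figures reproduce.

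**2. The regional claim at 1,300.** Table 4 gives regional half-widths of 1.69% (measles), 1.45% (hepatitis B) and 2.64% (CMV). Against the stated bound of ±2%, CMV fails with no further assumption.

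**3. Sample size at which measles reaches ±2%.** With half-width proportional to 1/√n:

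- from the regional row: 1,300 × (1.69/2)² = 928
- from the national row: 3,900 × (0.82/2)² = 656

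The two differ because Table 4 does not follow 1/√n exactly. National × √3 gives 1.42% for measles (stated 1.69%), 1.47% for hepatitis B (stated 1.45%) and 2.93% for CMV (stated 2.64%). The scaled figures are therefore approximate, and step 4 shows both.

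**4. Brussels under a population-size rule.** Assumption, not in the documents: Brussels holds 10–12% of the population. Then n = 3,900 × 0.10 to 0.12 = 390 to 468.

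| | Stated at 1,300 | Regional row × √(1,300/n), n = 468 to 390 | National row × √(3,900/n), n = 468 to 390 |
|---|---|---|---|
| Measles | 1.69% | 2.82–3.09% | 2.37–2.59% |
| Hepatitis B | 1.45% | 2.42–2.65% | 2.45–2.69% |
| CMV | 2.64% | 4.40–4.82% | 4.88–5.34% |

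With a wider assumed share of 8–15% (312–585 samples), the measles half-width scaled from the regional row is 3.45% to 2.52%.

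**5. Brussels under a literal density rule.** The documents give no inputs, so these are scenarios only. Let r be the assumed density of Brussels relative to the other areas.

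- Area = region, the other two equally dense: share = r/(r + 2). For r = 2, 5, 10, 20 this is 50%, 71%, 83%, 91%.
- Area = one of the 11 areas in the Appendix 3 dummy table: share = r/(r + 10). For r = 5, 10, 20 this is 33%, 50%, 67%.
- Quota per laboratory, all 52 taking part, b of them in Brussels: share = br/(br + 52 − b). For b = 2, r = 10 it is 29%; for b = 3, r = 15, 48%; for b = 5, r = 15, 61%; for b = 8, r = 20, 78%. With b = 1 and r = 5 it is 5/56 = 9%.

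The share depends almost wholly on inputs that the protocol does not state.

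**6. Direction of the conflict.** Suppose the literal rule gave Brussels half the samples (1,950), leaving 975 for each other region. The measles half-width would be 1.69 × √(1,300/1,950) = 1.38% in Brussels and 1.69 × √(1,300/975) = 1.95% elsewhere. That is the reverse of the wider Brussels interval that the Sample size section accepts.

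**The case against.** The strongest reply is that the word density is a slip for size. The sentence states its purpose, it makes the quotas depend on how many laboratories join, and the Sample size section itself speaks of population size. Read that way, the two main-text passages largely agree: Brussels gets fewer samples and wider intervals. Tubes and labels are supplied centrally, so no laboratory would apply the literal rule on its own. This is probably what was meant, and it softens the conflict. It does not make the written rule right. Even as population size, the rule remains a different criterion from practical constraints and laboratory numbers, and no regional figure settles which governs.

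Three stronger readings are tempting, and the documents do not support them.

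- A reader might infer that the density rule sends most samples to Brussels. This needs a density ratio, an area unit and a laboratory count by region, none of which is given. The listed scenarios run from 9% to 91%.
- A reader might infer that three allocation rules are in force at once. The main text takes the 3,900 from Appendix 5 but openly declines its regional split, so the equal split is text left unmarked, not a live rule.
- A reader might infer that the loss of regional precision is hidden. The Sample size section accepts wider intervals in Brussels and quotes no regional precision, and Table 4 labels its regional row as based on 1,300 per region.

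The planned post-stratification weights also answer part of the concern. They can correct the national estimate for spatial imbalance, but they cannot restore precision in an under-sampled region.

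**Conclusion.** The point holds. As written, the quota rule works against its own stated purpose and against the expectation for Brussels in the Sample size section. How far it would distort the allocation cannot be determined from the documents.

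Separately, the regional precision in Appendix 5 is not what the adopted plan delivers for Brussels. The claim of precision below ±2% at regional level fails for CMV even under the rejected equal split. For measles in Brussels it fails below about 930 samples when the regional row is scaled, or about 660 when the national row is scaled. With an assumed 390–468 samples, the measles half-width is roughly 2.4–3.1% instead of 1.69%. Those figures rest on the assumed 10–12% population share and on approximate 1/√n scaling. The national total of 3,900 is not in question here.

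**What to change.** Settle the following before quotas and tubes are sent out:

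1. In Sampling procedure, replace population density with population size in the sampled age range of the area served, and define the area. Reconcile this with the Sample size section so that one allocation rule remains.
2. State a planned number of samples for each region, and give any deliberate top-up for Brussels as a number.
3. In Appendix 5, mark the equal split and the Regional column of Table 3 as a scenario that was not adopted.
4. Recompute the Regional row of Table 4 separately for each region at its planned number, by the same simulation and not by scaling.
5. Withdraw the statement of regional precision below ±2% wherever it is not met. This already applies to CMV.

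The cost is protocol wording and one recomputed table row, with no extra samples. The downside is that precision for Brussels will look less favourable on paper.
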